#### 9.2.1 Pathology Review

A total of 26 unstained FFPE tumor tissue will be stored at each institution after enrollment. At the end of the study, all samples, including on-treatment biopsy samples, at participating institution will be batched and shipped to the Histopathology Shared Resource at the G-LCCC. Pathologic diagnosis will undergo central review by study dermatopathologist. A provided Haematoxillin & Eosin stained slide will be used to confirm physical characteristics of tumor samples and eligibility for the correlative studies. The following criteria are required for molecular analyses based on the TCGA Biospecimen Qualification Criteria:

1. Tumor nuclei are presented in  $\geq 60\%$  of the slide
2. Tumor necrosis is  $\leq 20\%$
3. In the case of frozen tissue submission, the samples must be continuously frozen with less than 30 minutes between devascularization and freezing.

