2.3 To determine progression-free survival (PFS), and overall survival (OS) in each cohort

2.4 To determine whether pre-existing immune cells infiltrate, as well as Ki-67 and PD-L1 expressing cells at the invasive tumor margin correlate with clinical response to a combination of CTLA-4 and PD-1 blocking therapy

2.5 To evaluate subject's cancer genomic landscape using whole exome sequence profiling, identify the mutational pattern, and the frequency of somatic mutations and their relationship to tumor response in MCM and ALM, as well as subject's cancer genomic landscape using whole exome sequence profiling and utilize bioinformatic tools to translate mutations in exomes to identify specific driver mutations in MCM and ALM

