## 9.2 Studies to be performed on tissue

All participants will have either formalin-fixed, paraffin embedded (FFPE) tissue or fresh tumor biopsy collected at baseline. Fresh tumor biopsies will be obtained from safely accessible locations. Preferred biopsies include excisional or punch biopsy; 14-16 gauge core needle biopsies are acceptable if these are not feasible.

Please refer to Laboratory Manual for detailed instructions on specimen collection, processing, storage and shipment.

Baseline tumor specimen from each patient will be divided for three different biomarker analyses  
 (i) Tumor Whole Exome Sequencing (WES) for analysis of mutational burden, mutational pattern, prediction of tumor neoantigen peptides that react to patient's Major Histocompatibility (MHC) class I molecules requires 8 unstained slides at 10microns thickness. (ii) Immunohistochemistry study and quantification of immune cells and PD-L1+ cells infiltration at the invasive tumor margin requires 10 unstained slides at 5 microns thickness. (iii) Baseline assessment of T-cell receptor (TCR) rearrangement of TILs using next-gen sequencing technique requires 8 unstained slides at 10-micron thickness. After the initial analysis, tumor blocks from each participant will be stored at the site in MRFBC Tissue Bank for potential later investigation.

Approximately 25% of patients enrolled in this protocol, n=15 (10 patients from MCM cohort and 5 patients from ALM cohort) are anticipated to have on-treatment fresh biopsies from safely accessible location during weeks 6, 7 or 8 into treatment. Each on-treatment biopsy will be

evaluated for CD8+, PD-L1+, and Ki-67+ cells at the invasive margin as a predictive biomarker of response (ii) TCR rearrangement in response to a combined immune checkpoint inhibitor therapy.

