#### 9.2.7 Assessment and Monitoring of T-Cell Receptor Rearrangement

Planned analyses include assessment of TILs T-cell receptor β-chain genes using ImmunoSeq® platform. The analyses will assess the baseline TCR recombination (unique TCR sequences, clonal frequency distribution, and TCR diversity) between variable (V), joining (J), and diversity (D) segments that result in unique sequences in the antigen-binding site, as well as the effect of combined immune checkpoint inhibitor therapy on V(D)J rearrangement of TCR. Specimens for TCR rearrangement assay will be batched and sent from G-LCCC to Adaptive Biotechnology for analyses at the end of the study. Data analysis will be performed by [name] at G-LCCC.

Please refer to Laboratory Manual for detailed instruction on specimen collection, processing, storage and shipment.

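### The 60% tumor-nuclei requirement is not limited to exome and RNA sequencing, so as written it can screen samples out of the T-cell-receptor study on a feature expected to track response

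*Combined protocol and SAP*

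**What the plan says.** Section 9.2.1 describes central pathology review at the end of the study. A stained slide "will be used to confirm physical characteristics of tumor samples and eligibility for the correlative studies". The next sentence reads "The following criteria are required for molecular analyses based on the TCGA Biospecimen Qualification Criteria", and the list begins "Tumor nuclei are presented in" at least 60% of the slide, followed by a ceiling of 20% on necrosis. The same section sends on-treatment material through this review: "all samples, including on-treatment biopsy samples, at participating institution will be batched and shipped".

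TCR profiling uses slides from the same baseline specimen. Section 9.2 says "Baseline assessment of T-cell receptor (TCR) rearrangement of TILs using next-gen sequencing technique requires 8 unstained slides at 10-micron thickness". Section 9.2.7 sets out what is measured: "The analyses will assess the baseline TCR recombination (unique TCR sequences, clonal frequency distribution, and TCR diversity" and the effect of therapy on the rearrangement. Objective 2.7 (exploratory) treats clonal change from before to after treatment as a correlate of response. Section 10.3.1 lists CD8+ infiltrate level and TCR clonality as separate candidate factors, and compares responders with non-responders by Fisher's exact or Wilcoxon rank sum test.

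About 15 on-treatment biopsies are expected, 10 mucosal and 5 acral (9.2 and Appendix G; an Appendix F footnote prints 25 beside the same 10 and 5). Macrodissection is described for exome (9.2.3) and RNA (9.2.4) work, but not for TCR (9.2.7). No comparison of excluded with included samples is planned.

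**The concern.** For exome sequencing, non-tumor DNA dilutes the signal, so a minimum tumor content is sensible. For TCR sequencing the lymphocytes are the signal, and the same minimum works against the assay. The protocol's own background (1.8.4) says that denser pre-treatment CD8+ infiltrate predicted better outcome on PD-1 blockade, and that response was associated with clonality of the infiltrate. A rule that drops samples for low tumor content can therefore select on something the protocol expects to be related to outcome. The on-treatment set is small, and each biopsy lost also loses a before/after TCR pair. A lesion that is regressing at weeks 6 to 8 may hold little tumor, so the lost pair may well come from a responder.

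**Working it through.** **1. The plan's own figures.** Section 10.2 gives 39 evaluable mucosal patients, 25% against 45%, one-sided 10%, 90% power. With n = 39 the exact binomial rule is at least 14 responses: alpha 0.086, power 0.905. Enrolment is 39/0.8 = 48.75, so 49. Both reproduce, and neither depends on the TCR study. The 60% criterion has no stated failure rate, and the TCR study has no sample size.

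**2. Which assays are covered.** The criterion governs molecular analyses, a term that is not itemised. TCR profiling is described as next-generation sequencing on slides of the same specimen and is not exempted. Covering it is the plain reading, but it is an inference.

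**3. What the threshold does on each reading.**
- Share of nuclei: tumor at 60% or more means lymphocytes plus stroma at 100 − 60 = 40% or less in every retained sample. The upper tail of infiltrate is cut off.
- Area of slide: lymphocytes mixed within tumor do not fail. No truncation of baseline infiltrate can be derived.
- Either reading: an on-treatment sample with little residual tumor fails.

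**4. Direct truncation (infiltrate quantity only).** Normal approximation, top share removed *assumed*. With s the remaining SD ratio, r' = r·s / √(1 − r² + r²s²).

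| Removed from top | s | r = 0.50 becomes | r = 0.30 becomes |
|---|---|---|---|
| 20% | 0.76 | 0.40 | 0.23 |
| 30% | 0.70 | 0.38 | 0.22 |
| 40% | 0.65 | 0.35 | 0.20 |

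**5. Indirect selection (closer to clonality).** Let k = 1 − s², a = correlation of infiltrate with clonality (*assumed* 0.3 to 0.5) and b = correlation of infiltrate with response (*assumed* 0.15 to 0.3). Then r' = (r − abk) / √[(1 − a²k)(1 − b²k)]. Example with 40% removed, a = 0.5, b = 0.3: k = 1 − 0.65² = 0.578, and r' = (0.50 − 0.087)/√(0.856 × 0.948) = 0.46. Over 20 to 40% removed, 0.50 becomes 0.46 to 0.50, and 0.30 becomes 0.24 to 0.29.

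**6. Illustrative simulation, share-of-nuclei reading.** All inputs are *assumed* except the total of 49 + 24 = 73 enrolled and the 45% response rate, which is the plan's alternative: mean immune share of nuclei 15, 25 or 35% (beta distribution, concentration 5); stroma 0, 15 or 30% of the remainder; odds ratio for response 2 per SD of immune share; two-sided 5% Wilcoxon test.

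| Quantity | Range over the nine scenarios |
|---|---|
| Most infiltrated quartile excluded | 30 to 100% |
| Least infiltrated quartile excluded | 0 to 42% |
| SD of infiltrate, retained relative to all | 0.42 to 0.71 |
| Response rate, retained samples (all: 45%) | 29 to 42% |
| Power for infiltrate against response, no floor | 0.69 to 0.79 |
| Same, with floor | 0.06 to 0.44 |

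These results concern infiltrate quantity. They show direction under the assumptions and do not estimate the effect on clonality.

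**The case against.** The case for leaving the text alone has substance.

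- *Scope.* Criterion 3.1.3 names multiplex immunohistochemistry apart from nucleic acid analyses and glosses the latter as exome sequencing. Section 9.2 lists TCR as a separate analysis with its own slides. A narrower intent is possible, and the separate Laboratory Manual may hold an assay-specific rule. This stands as a reason for caution, but 9.2.1 itself still exempts nothing.
- *Wrong variable.* A reader might infer that the rule truncates the very variable the TCR study relates to response. The documents do not support that: 9.2.7 measures unique sequences, clonal frequency and diversity, not lymphocyte quantity. Selection is on a correlated variable, with the unique-sequence count the nearest to quantity. The step 4 figures therefore do not carry over to clonality.
- *Objective 2.4.* A reader might also infer damage to the aim "To determine whether pre-existing immune cells infiltrate, as well as Ki-67 and PD-L1 expressing cells at the invasive tumor margin" correlate with response. That infiltrate is measured by immunohistochemistry, which the sentence on molecular analyses does not name. Coverage follows only if the preceding general sentence on correlative-study eligibility carries the 60% rule to every assay. That reading is possible, but it is not stated.
- *Direction.* Stroma-rich, lymphocyte-poor samples fail too. Selective loss of responders, or on-treatment biopsies being hit hardest, is plausible, but no figure in the documents supports either.
- *Consequence.* Objective 2.7 is exploratory, and 10.3.1 calls these analyses hypothesis-generating.

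These points limit certainty and size. They do not answer the regressing on-treatment lesion, which fails whether the 60% is of nuclei or of area.

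**Conclusion.** The point holds as a low-priority flaw in a stated rule. As written, 9.2.1 applies a tumor-content floor to an assay that targets non-tumor cells. It can exclude heavily infiltrated baseline samples (only if the floor means share of nuclei) and regressing on-treatment lesions (on either reading), and so bias or thin the objective 2.7 analysis. This rests on TCR sequencing being among the molecular analyses, which is the plain reading but not an explicit statement.

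The size cannot be derived. On assumed inputs, indirect selection lowers a true correlation only modestly (0.50 to between 0.46 and 0.50), and the larger losses apply to infiltrate quantity.

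A reader might infer that the primary response-rate analysis is affected. The 39/49 calculation is not. Section 10.1 replaces patients whose block holds too little tumor, but nothing says that the 60% criterion decides this. If it were used that way, the selection could reach the primary population, so the text should rule it out.

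**What to change.** In 9.2.1:

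1. State that the 60% criterion governs exome and RNA sequencing only, and whether it means share of nuclei or area of slide.
2. Do not apply it to TCR sequencing or multiplex immunohistochemistry. Use specimen quality control suited to each, for example T-cell or DNA yield for TCR.
3. Record tumor-nuclei percentage for every sample, and report excluded samples by assay, time point and response status.
4. State that failing this criterion does not count as too little tumor for patient replacement under 10.1.

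The cost is a few sentences and one recorded value per sample, settled before the end-of-study batch goes to review. The downside is that a few samples with low tumor content enter the TCR assay. The recorded percentage allows the analysis to be repeated with it as a covariate or without those samples.

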#### 9.2.2 Tumor Whole Exome Sequencing

At the end of the study, unstained slides will be batched and shipped to [name] at University of Colorado where exome sequencing will be performed.

#### 9.2.3 Assessment of Tumor's Mutational Burden and Driver Mutations

Analysis will utilize matched paired of (i) tumor, and (ii) normal adjacent stromal tissue from pre-treatment samples. Tissue dissection will be done by means of macrodissection. Paired normal tissue will serve as control and reference sequence for each patient's tumor and differentiation of germline mutations/polymorphisms from true somatic mutations. Tumor and normal stromal tissue will undergo DNA extraction according to standard FFPE DNA extraction protocol. DNA fragmentation, DNA library preparation, exome enrichment, automated cluster generation, paired-end sequencing, and base calling will be performed at University of Colorado at the end of the study.

Human exome sequencing from gDNA will include initial DNA sample QC using NanoDrop and Qubit. Exome sequences will be captured using the Agilent SureSelect Exome enrichment kit, along with associated QC, and libraries constructed using standard Illumina library preparation. Samples will be sequenced on an Illumina HiSeq2000 using PE100-125bp read length chemistry, designated 400x average coverage for the cancer and 200x for normal exomes with approximately 9-11 Gb output. Standard exome bioinformatic analysis will include mapping and alignment (BAM file), QC, coverage, sequence variation (SNPs/Indel report (.VCF file)), VCF annotations, functional prediction, and population frequency. Deliverable will include raw data FASTq and analysis files (.VCF)

Data cleanup, variant discovery, annotation, and evaluation will be performed at University of Colorado. Mutational load will be quantified as the number of non-synonymous somatic mutations per megabase (MB). Raw and annotated exome sequencing data will be available at MRFBC Cloud library for future data mining and comparison.

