#### **Human Leukocyte Antigen Testing**

High-resolution Human leukocyte antigen (HLA) typing information from each participant will be extracted from whole exome sequencing data obtained from whole blood (genomic DNA). The analysis will be performed at University of Colorado ([name]) at the end of the study.

Please refer to Laboratory Manual for detailed instruction on specimen collection, processing, storage and shipment.

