### 9.3 Studies to be performed on blood

Peripheral blood samples will be collected on all patients prior to initiation of checkpoint inhibitors therapy and during treatment.

Serum will be used in circulating nucleic acids analyses. One additional 10ml tube of blood at each specimen collection step has been incorporated into the protocol to exclusively store as a part of MRFBC Virtual Repository and for future research.

At the conclusion of the therapy for each patient, specimens should be batched and transported to G-LCCC-Histopathology Shared Resource (HTSR) c/o [name] at the provided address for assessment of circulating cell-free nucleic acids. Circulating nucleic acid analyses will be done under the direction of [name] at GU-LCCC.

Please refer to Laboratory Manual for detailed instruction on specimen collection, processing, storage and shipment.

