### 9.3.1 Assessment of Pretreatment and Serial Levels of Circulating Cell-Free Nucleic Acids

All patients will have plasma and serum collected at pre-treatment, every 6 weeks on-treatment, and at PD. Guidelines for isolation of plasma and serum are outlined in Section 9.3. Each sample will be linked to the corresponding tumor and labeled with non-identifiable coding system designated for each tumor.

Information on mutant DNA enriched in each tumor will be extracted from WES analyses. The analysis will assess circulating cell-free mutant DNA from the top most enriched mutations in each patient's tumor, in addition to a panel of cancer related genes. Circulating cell-free mutant DNA analysis will be performed on Illumina HiSeq system with TruSeq Nano Sample Preparation Kit (or equivalent system) to detect and quantify the circulating mutation load per ml of serum. The frequency of circulating mutant DNA will be assessed at baseline, at 6 weeks interval, and at RECIST-defined disease progression. The kinetics of circulating cell-free mutant DNA compared to baseline will be compared with radiographic response (per RECIST v.1.1) to establish the relationship between circulating mutant DNA burden and response to combined immune-checkpoint blockade.

Serum samples from each patient may be used to analyze for circulating non-coding RNA (i.e. miRNA) and exosomal substrates (i.e. protein, miRNA, snRNA)

We will attempt to establish predictive circulatory biomarker that could separate responders from non-responders in MCM and ALM cohorts

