## Appendix G

### Specimen Submission Guidelines

Baseline tumor: tumor block or 26 unstained FFPE slides from primary or met; preferred excisional or punch (if not possible 14-16 gauge core needle)						
Correlative Study	Sample required at each time point	Baseline	6-8 wks  after tx	Every 6 wks during tx	Disease Progression	Shipping/ Storage for Future Use
Baseline correlative Studies on Tissues	Tumor block or 16 unstained FFPE tumor tissue slides at 10-micron	XX				Ship to GU-LCCC-HTSR ([name]) at the end of the study. Leftover specimens (if any) stored at GU-LCCC-HTSR & placed in MRFBC VR for future use
	Tumor Block or 10 unstained FFPE tumor tissue slides at 5-micron	XX				
(Optional) On-treatment correlative Studies on Tissues	1. Frozen tumor embedded in OCT at-80c 2. FFPE tumor block		XX			Ship to GU-LCCC-HTSR ([name]) at the end of the study. Leftover specimens (if any) stored at GU-LCCC-HTSR & placed in MRFBC VR for future use

1 Expect 25% of patients (N=15; 10 MCM and 5 ALM patients) to consent to on-treatment biopsies

2 Blood samples will be taken  $\leq$  7 days prior to treatment

3 Specimens should be batched shipped to GU-LCCC-GESR at the conclusion of therapy for each patient. (at the end of the trial)

Correlative Study	Sample required at each time point	Baseline	3 wks  after tx	Every 6 wks during tx 	Disease Progression or at the end of study	Shipping/ Storage for Future Use 
High-resolution HLA typing	CPT TM Mononuclear cell preparation tube blood	XX; 10ml				Ship to GU-LCCC-HTSR ([name]) at the end of the study.
Blood Correlates	Blood in Cell-Free DNA BCT ® tubes (Streck TM ) -Red-top blood -CPT TM Mononuclear cell preparation tube blood	XX  20ml blood in Cell-Free DNA BCT ® tubes; 10ml red-top blood, 10ml CPT TM tube blood (collect within 7 days prior to treatment)		XX  20ml blood in Cell-Free DNA BCT ® tube; 10ml red-top blood; 10ml CPT TM tube blood	XX  20ml blood in Cell-Free DNA BCT ® tube; 10ml red-top blood; 10ml CPT TM tube blood	Ship to GU-LCCC-HTSR ([name]) at the end of the study.; Leftover specimens (if any) stored at GU-LCCC-GESR & placed in MRFBC VR for future use

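### Adjacent stroma is the only named germline reference for somatic calling; the planned blood exome, named only for HLA typing, would be a safer one

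*Combined protocol and SAP*

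**What the plan says.** Section 9.2.3 pairs each pre-treatment tumor with adjacent stromal tissue, separated by macrodissection, and gives that tissue the germline role: "Paired normal tissue will serve as control and reference sequence for each patient's tumor and differentiation of germline mutations/polymorphisms from true somatic mutations". Depth is "designated 400x average coverage for the cancer and 200x for normal exomes". Mutational load is the count of non-synonymous somatic mutations per megabase. On the calling itself the section says that "Data cleanup, variant discovery, annotation, and evaluation will be performed at University of Colorado". It lists QC in general terms but names no caller, no rule for rejecting a variant seen in the normal, and no check for tumor DNA in the normal.

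Section 9.2.1 qualifies a sample when "Tumor nuclei are presented in" at least 60% of the slide. It sets no upper limit on tumor content in the dissected stroma.

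The Human Leukocyte Antigen Testing text under 9.2.5 says that HLA type "will be extracted from whole exome sequencing data obtained from whole blood (genomic DNA"). That work and the tumor exome sequencing are assigned to the same university, both at the end of the study. HLA typing is the only use stated for the blood exome, and its depth is not given. Appendix G has a baseline row for "High-resolution HLA typing", but the tube listed there is a CPT mononuclear-cell tube. Under 9.3, "Peripheral blood samples will be collected on all patients prior to initiation of checkpoint inhibitors therapy".

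**The concern.** The normal tissue is cut by macrodissection from the same tumor-rich material as the tumor, so some tumor cells in it are plausible. A somatic variant that also appears in the normal can be taken for a germline variant and dropped. Blood does not share this route of contamination.

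The reported averages in these tumors are small (12 to 66 non-synonymous variants, section 1.8.2), and section 1.8.5 asks whether low burden means low neoantigen load. A downward artefact would look like the expected biology. The results at stake are objective 2.5, the responder comparisons in 10.3.1, the log rank analysis of mutational load in 10.3.2, and the neoantigen prediction in 9.2.5.

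**Working it through.** The plan states no figure for carry-over or its effect, so there is none to reproduce. The calculation below shows only how far the answer depends on what is not stated.

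**Inputs from the documents.** Depth is 400x for tumor and 200x for normal (9.2.3). The minimum tumor nuclei on the slide is 60% (9.2.1).

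**Assumed inputs.** These are the tumor-cell share in the stroma, c; the share of tumor cells carrying the variant, f (the same in carried-over cells); tumor purity after dissection, 60% or 80%; heterozygous diploid variants; and both calling rules.

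**Rule A: reject any variant with at least k reads in the normal.** For a clonal variant (f = 1) and c = 5%, the expected variant fraction in the normal is 0.05/2 = 0.025, or 200 × 0.025 = 5 reads. The loss is P(X ≥ k) with X ~ Binomial(200, 0.025):

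| k | Loss |
|---|---|
| 3 | 88% |
| 6 | 38% |
| 10 | 3% |

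If all variants were of this kind, 12 and 66 true variants would become 12 × 0.121 = 1.5 and 66 × 0.121 = 8.0 at k = 3, but 11.6 and 64.0 at k = 10.

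**Rule B: keep a variant if tumor and normal differ (one-sided Fisher p < 0.001).** Tumor reads ~ Binomial(400, purity × f/2); normal reads ~ Binomial(200, c × f/2).

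- Clonal variant, 60% purity, c = 5%: expected reads are 400 × 0.30 = 120 against 200 × 0.025 = 5. The loss is under 0.1%, and it stays there at c = 10%.
- Variant in half of the tumor cells, 60% purity: the loss is 0.03% at c = 5% and 1.25% at c = 10%.
- Variant in a quarter of the tumor cells, 60% purity: expected reads are 400 × 0.075 = 30 in tumor, against 1.25 in the normal at c = 5% and 2.5 at c = 10%. The loss is shown below.

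| Quarter of tumor cells (f = 0.25) | c = 0 | c = 5% | c = 10% |
|---|---|---|---|
| 60% purity, p < 0.001 | 0.3% | 16% | 40% |
| 60% purity, p < 0.01 | 0.0% | 2.4% | 12% |
| 80% purity, p < 0.001 | 0.0% | 1.5% | 8% |

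**Reading.** This mechanism can only lower the count. The size depends on carry-over, rule and purity together, and moving any one of them within a reasonable range changes the conclusion. With a blood reference, c from adjacent tissue is 0 and this loss disappears, leaving aside tumor DNA or cells circulating in blood.

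**The case against.** A matched normal from every patient at 200x is a legitimate design, and nothing in the documents shows that carry-over will occur. The 60% floor qualifies tumor samples; it does not describe the stroma after dissection. That stands, so the point is conditional.

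The laboratory manual (Appendix H) is a separate document that was not available, and a few pages were missing from the copy reviewed. A reader might infer that no tumor-in-normal check is planned. The documents do not support that: the check is unstated in a section that does not name the caller either.

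The large losses come from a rule that ignores the tumor reads, which the plan nowhere suggests. Under a paired rule clonal loss is about zero, and the subclonal losses shrink quickly at 80% purity. This also stands.

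Other errors push the load upward, such as FFPE artefacts or germline variants missed at low local depth in the normal. Stroma fixed in the same way helps against the artefacts, which is a good reason to keep it.

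A reader might also infer that a load biased low must weaken its association with response. It need not. Section 10.3.1 uses the Wilcoxon rank-sum test, and a common proportional loss largely preserves ranks apart from thinning noise. Material weakening needs a loss that varies between patients. Similarly, section 9.3.1 says "Information on mutant DNA enriched in each tumor will be extracted from WES analyses", but its targets are the most enriched variants plus a cancer-gene panel, and a paired rule hardly loses high-fraction variants.

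Finally, raw exome data are kept, so calls could be redone. That helps only if a blood exome of sufficient depth exists, and its depth is not stated.

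**Conclusion.** The point holds as a design improvement. The plan names a reference that is open to tumor carry-over and leaves a planned, better-placed one unused for this purpose. If carry-over occurs, mutational load is lowered by this route, mainly through subclonal variants under a paired caller. The size is unknown, from about 0% to most variants under the assumptions shown. The stronger statement, that reported load will be substantially too low, is not supported, because neither the carry-over nor the net bias of the pipeline can be established from the documents.

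The primary ORR test is untouched. Objective 2.5 is secondary in section 2.0, but 10.2 lists the relation of mutational frequency to response as exploratory, and 10.3.1 calls these analyses hypothesis-generating. Priority is therefore low to moderate.

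**What to change.** In 9.2.3:

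- Name the blood exome already planned under 9.2.5 as the primary germline reference, at the 200x stated for normal exomes.
- Keep the stromal exome as a same-fixation control for FFPE artefacts.
- Report a tumor-in-normal estimate for each stromal sample.
- Flag variants whose status differs between the two normals.

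If the laboratory manual already contains a calling rule or contamination check, cross-refer to it. Reconcile the whole-blood source in the HLA text with the CPT mononuclear-cell tube in Appendix G. Settle this before the end-of-study sequencing, when depth becomes fixed.

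The cost is wording in the protocol and laboratory manual, some extra analysis, and filtering of blood-specific variants. No new sample is needed. If the HLA exome was planned below 200x, deeper blood sequencing is needed for up to 49 + 24 = 73 patients.
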